6.2 Methods for minimising bias

This study is a non-randomized and open label observational study.

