6.2.2 Blinding procedures

Not applicable.

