7.2 Recruitment and screening

There will be a consecutive ongoing recruitment of patients and healthy subjects attending routine follow-ups through the involved investigators in daily clinical practice at Department of Ophthalmology, Inselspital, Bern. Recruitment will last from October 2021 to November 2023. Subjects will be given enough time (hours to days) to consider and to council with relatives and experts. No screening requirements is necessary (laboratory or other diagnostic tests). There will be no payment or compensation given to subjects.

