7.3 Assignment to investigation groups

The recruited participants will be assigned to the diagnostic categories mentioned at 6.1. or categorized as healthy. No randomization is planned.

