9. CLINICAL INVESTIGATION ASSESSMENTS

9.1 Clinical investigation flow chart(s) / table of clinical investigation procedures and assessments

There will be a consecutive ongoing recruitment of patients and healthy subjects attending routine follow-ups through the involved investigators in daily clinical practice at Department of Ophthalmology, Inselspital, Bern. Recruitment will last from October 2021 to November 2023. Patients, who fulfilled the indication of either SD-OCT or fluorescein angiography imaging for diagnosis of retinal/optic nerve disease will be included and additional imaging will be performed with the High-Res-OCT.

Subject	Initial imaging with High-Res-OCT
Healthy volunteers	X ₁
Patients with retinal/optic nerve disease	X ₁
X =mandatory imaging session. ¹ routine imaging with either SD-OCT, fundus photography or fluorescein angiography according to clinical routine	

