9.2 Assessments of outcomes

[figure not shown]

Fig. 2: Switching the device on and off

- ① Isolating transformer
- ② Power supply
- ③ PC
- ④ Monitor

The high-quality images of the retinal structures acquired with the SPECTRALIS HighRes-OCT ® will be obtained as follow:

- Power on the unit and log on
- Enter, find, and modify patient identifying data
- Clean surfaces that contact patient
- Position patient with the device, including moving the patient, the device, the table height, and the patient's chair
- Select and acquire scan
- Review and save scan or try again
- Generate reports using available reporting protocols
- Review reports for completeness
- Output reports
- Archive data
- Turn off the unit

The operators will be trained Heidelberg Engineering GmbH - 8105 Regensdorf – Switzerland, which will also calibrate the medical device and offers maintenance and support.

The data analysis will be performed by the investigator with the appropriate professional training or experience in the use of ophthalmic imaging equipment.

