9.2.1 Assessment of primary outcome

The sensitivity and specificity of the High-Resolution OCT to diagnose the presence/absence of pathological changes in the retina/optic nerve in comparison to conventional imaging modalities will be assessed as a primary outcome. The following pathological changes will be assessed: intraretinal or subretinal fluid, pigment epithelial detachment, epiretinal membrane, substance defect, drusen, hyperreflective foci, atrophy, neovascularization, choroid abnormalities, scars, optic nerve swelling and ischemia. For each of these pathological changes a binary outcome will result. Additionally, study participants will be asked to consent to prospective collection of clinical and demographic data, to correlate findings of High-Res-OCT imaging to subsequent clinical course.

There is no need to be in a particular posture before the examination in order to obtain high quality images. The participants will be in a sitting position during the examination during approximately 30-60 seconds per eye. In case the measurement needs to be repeated, no waiting period will be necessary. A repeated measurement needs to be recorded in the CRF.

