9.2.2 Assessment of secondary outcomes

- To evaluate whether pathological changes seen in SD-OCT or color fundus photography correlate with changes seen in High-Res-OCT, a binary readout will be used, i.e. pathology present yes/no.
- Subgroup analysis will be performed with patients suffering from diabetic retinopathy, artery and vein occlusion, retinal detachment, glaucoma, optic nerve neuropathy, hereditary retinal diseases, age related macular degeneration, retinal changes from arterial hypertension and uveitis. For this purpose a quantification and classification of the pathological changes in relation to each disease will be performed, among them; Drusen classification according to Age-Related Eye Disease Study (AREDS) ²⁷, neovascularization, bleeding, ischemia, atrophy, exudate, retinal thickness, intra-subretinal fluid, pigment epithelial detachment (PED) and epiretinal membrane ^{28,29}. In order to compare these groups with conventional imaging and controlling for some degree of variation due to age, patients included in subgroup analysis will be compared to a pool of healthy subjects.
- Evaluation of the intra- and inter-reader reproducibility in the diagnosis using High-Res-OCT. This will result in a binary outcome (diagnosis present or absent). The evaluation of the inter-reader reproducibility in healthy subjects with High-Res-OCT will be assessed. For this purpose a senior physician, a resident and an expert physician will subsequently analyze the images.
- Furthermore the quality of the segmentation of the retinal layers, i.e. the discrimination capacity between the different layers (internal limiting membrane, retinal nerve fibre layer, ganglion cell layer, inner plexiform layer, inner nuclear layer, outer plexiform layer, outer nuclear layer, external limiting membrane, photoreceptor layer, retinal pigment epithelium, Bruch's membrane, choriocapillaris and choroidal stroma) will be assessed, especially in the healthy group. For this purpose, a binary outcome will also result, i.e. discrimination between each layer possible, yes or no.

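### No masking of image readers is specified: the plan marks blinding as not applicable, although the primary outcome is a human yes/no call on same-day images of known patients

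*Combined protocol and SAP*

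**What the plan says.** Section 6.2 (Methods for minimising bias) consists of one sentence: "This study is a non-randomized and open label observational study". Section 6.2.2 (Blinding procedures) reads "Not applicable", and section 6.2.3 (Other methods for minimising bias) has the same entry.

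The passages that describe who sees what are these:

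- **Recruitment (7.2).** Participants are people "attending routine follow-ups through the involved investigators in daily clinical practice".
- **Grouping (7.3).** "The recruited participants will be assigned to the diagnostic categories mentioned at 6.1. or categorized as healthy".
- **Imaging (9.1, 9.3, 9.3.1).** Patients qualify through a clinical indication for conventional imaging, and "additional imaging will be performed with the High-Res-OCT". Screening, baseline and imaging fall on one day. Routine imaging and High-Res-OCT are listed under the same visit.
- **Reading (9.2, 9.2.1, 9.2.2).** "The data analysis will be performed by the investigator". On the primary outcome: "For each of these pathological changes a binary outcome will result". For reproducibility, "a senior physician, a resident and an expert physician will subsequently analyze the images".
- **Forms (12.1.1, 12.1.2).** All investigators may enter data on both study forms. One form holds the diagnosis; the other covers SD-OCT and angiography.

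**The concern.** An open-label, unrandomised design describes how participants are handled. It does not make masked reading of stored images inapplicable. Here the endpoint is a subjective call for each lesion type, and the people who recruit and classify participants may also be the people who read the scans.

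The direction of the risk matters because of the form of the claim. Sections 11.2 and 11.4 seek to exclude a difference of more than 10% in favour of conventional imaging. There are two routes by which unmasked reading could weaken that test:

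1. **Carry-over between modalities.** If a finding seen on the conventional image prompts a positive call on High-Res-OCT, or if calls drift together in both directions, the observed deficit shrinks and a false claim becomes more likely. Carry-over only from High-Res-OCT to the conventional read widens the deficit and is conservative.
2. **Knowledge of the disease group.** This needs no reading order. If it rescues the same share of missed lesions on both devices, both sensitivities rise and the gap between them narrows.

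The secondary outcomes in 9.2.2 are exposed too. Readers who know that a subject is healthy, or who know a colleague's call, can agree for reasons unrelated to the image.

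**Working it through.** **Is there a masking rule anywhere?** The provisions that might be taken for one do not serve that purpose.

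- Coded participant numbers (2.7, 12.1.1, 12.2) protect confidentiality. They are not described as hiding the diagnosis or conventional results from readers.
- The three readers in 9.2.2 serve reproducibility, and no rule requires them to read independently.
- Central data review (12.2.4) and the study-independent monitor (12.3) check completeness, accuracy and compliance.
- Consecutive recruitment (7.2) bears on selection, not on reading.

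Unmasked reading is therefore permitted, though not prescribed. The plan offers no figure on this point to reproduce. What follows is an illustration of size.

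**Inputs from the plan.** Margin 10%, one-sided 95% interval and conventional accuracy 90% (11.2); 9 disease groups × 50 = 450 patients (6.1).

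**Inputs assumed, not in the plan.** An independent reference standard; both reads available on all 450; true High-Res-OCT sensitivity 80%, so the deficit lies exactly at the margin; independent errors.

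**Test.** Let b = P(conventional +, High-Res-OCT −), c = P(conventional −, High-Res-OCT +) and d = b − c. The claim is made if d + 1.645 × √((b + c − d²)/n) < 0.10.

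**Masked reads.** b = 0.90 × 0.20 = 0.18 and c = 0.10 × 0.80 = 0.08, so d = 0.10. SE = √((0.26 − 0.01)/450) = 0.0236. The false-claim rate is Φ(0 − 1.645) = 5% (simulated 5.2%).

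**One-way carry-over of 25%, conventional to High-Res-OCT.** A quarter of b becomes positive on both: b = 0.135, c = 0.08, d = 0.055. SE = √((0.215 − 0.0030)/450) = 0.0217. The rate is Φ(0.045/0.0217 − 1.645) = Φ(0.43) = 67% (simulated 66.5%).

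**Group knowledge recovering 25% of misses on both devices.** Sensitivities become 0.90 + 0.25 × 0.10 = 92.5% and 0.80 + 0.25 × 0.20 = 85.0%, so d = 0.075.

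False-claim rates by simulation (200,000 replicates per cell):

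| Route | 10% | 25% | 50% |
|---|---|---|---|
| Conventional to High-Res-OCT, positives only (n = 450) | 20% | 66.5% | 99.8% |
| Symmetric (n = 450) | 12% | 34% | 90% |
| High-Res-OCT to conventional only (n = 450) | 2.5% | 0.6% | 0.03% |
| Group knowledge, equal on both devices (n = 450) | 12% | 33% | 88% |
| Specificity, 90% v 80%, group knowledge clears false positives on both devices (n = 100 healthy) | 8% | 15% | 40% |

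**Sensitivity to the assumptions.**

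- Section 9.1 asks for only one of the comparators, so complete pairs may be fewer. With 300 pairs, one-way carry-over gives 16/53/98%, symmetric 11/27/78% and reverse 2.9/1.0/0.1%.
- With positively correlated errors (cells 0.76/0.14/0.04/0.06, n = 450), one-way gives 19/63/99.7%, symmetric 14/44/96% and reverse 3.6/1.7/0.3%.
- With a true 15-point deficit (75%), 50% carry-over and 450 pairs, the claim is made in 92% of trials one-way, 41% symmetric and 0% reverse.

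**The case against.** The absence of a masking rule is not in dispute. The objections concern strength and reach, and several of them stand.

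- **The one-way row is an upper case.** It lets the conventional result only add positives. A reader who conforms to a positive finding may also conform to a negative one. If both discordant cells move to agree with the conventional read, the rates are about 12/34/90%, the same as the symmetric row. The inflation remains.
- **The cases sit at or beyond the margin.** Section 11.2 assumes no true difference. At 90% v 90% with 450 pairs and independent errors, the claim succeeds about 99.95% of the time, so contamination would barely change it. If High-Res-OCT is truly better, symmetric carry-over or equal recovery of misses would hide its advantage. This is correct: unmasked reading does not always favour the new device. A false-claim rate is nevertheless properly judged at the margin.
- **The figures need an independent reference standard.** If conventional imaging also served as the reference, this calculation would not apply. That is so, and it limits the figures but not the point.
- **No passage names the primary reader.** The data analysis in 9.2 need not mean image reading, and permission to enter data is not proof that a reader sees the diagnosis. The separate procedures mentioned in section 12 might contain reading rules. They would not cure a plan that declares blinding inapplicable.
- **Group masking is imperfect, and arguably unwanted.** Some diseases show on the scan itself, and reading with clinical context is a defensible target when the aim is diagnosis in individual patients. This bears on withholding the diagnosis. It does not bear on withholding the comparator result, because the plan's aim includes making comparators unnecessary.

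**Conclusion.** The concern holds. The plan declares blinding inapplicable for a subjective primary outcome and leaves readers free to know the same-day conventional findings and the diagnosis. This should be fixed: it touches the primary comparison, and once reads have been made unmasked no analysis can repair them, only a re-read of the images.

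Confidence is high that the rule is missing. The size is conditional. Under the assumptions stated, 10% carry-over takes a 5% false-claim rate to about 12% (symmetric) or 20% (one-way, the upper case), and larger carry-over does much more. The reverse direction is conservative. With no reading order stated, the plan does not settle which direction would apply.

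**What to change.** Replace the entries in 6.2.2 and 6.2.3, and carry the same rules into 9.2 and 9.2.2:

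1. Readers have no access to the other modality's images or findings. The modalities of one participant are read in separate sessions with a stated interval. This is the essential element.
2. All study images (High-Res-OCT, SD-OCT, fundus photography, angiography) are read under coded identifiers, with patients and healthy subjects mixed in random order.
3. Readers do not see the diagnosis, group, chart or other readers' calls. Where the reader pool allows, nobody reads participants they recruited or treated.
4. Calls are locked in REDCap, which already keeps an audit table (12.2.2), before any unmasked or consensus review.

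The cost is protocol wording, image coding and extra reading sessions for about 550 participants with one or both eyes imaged, which is real reader time. No new visits or procedures are needed, and no new readers if those already foreseen in 9.2.2 are used. Masking will be partial: the modality stays recognisable, some diseases are evident on the image, and a treating clinician may recognise an unusual case. The report should say so.

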6.2.1 Randomisation

No randomization is planned.

6.2.2 Blinding procedures

Not applicable.

6.2.3 Other methods for minimising bias

Not applicable.

6.3 Unblinding Procedures (Code break)

Not applicable.

7. CLINICAL INVESTIGATION POPULATION

7.1 Eligibility criteria

Subjects fulfilling all of the following inclusion criteria are eligible for the investigation:

- Informed Consent signed by the subject
 - Patients and healthy subjects from the Department of Ophthalmology, University Hospital Bern requiring conventional imaging for eye disease
 - Patients of 18 years or older

The presence of any one of the following exclusion criteria will lead to the exclusion of the subject

- Patients not willing or able to sign informed consent
- Patients younger than 18 years
- Contraindication and limitation of the MD as described in the instructions for use: Patients with epilepsy.
- Vulnerable subjects (except the objectives of the investigation concern vulnerable subjects specifically),
- Inability to follow the procedures of the investigation, e.g. due to language problems, psychological disorders, dementia, etc. of the subject
- Participation in another investigation with an investigational drug or another MD within the 30 days preceding and during the present investigation
- Enrolment of the PI, his/her family members, employees and other dependent persons

7.2 Recruitment and screening

There will be a consecutive ongoing recruitment of patients and healthy subjects attending routine follow-ups through the involved investigators in daily clinical practice at Department of Ophthalmology, Inselspital, Bern. Recruitment will last from October 2021 to November 2023. Subjects will be given enough time (hours to days) to consider and to council with relatives and experts. No screening requirements is necessary (laboratory or other diagnostic tests). There will be no payment or compensation given to subjects.

7.3 Assignment to investigation groups

The recruited participants will be assigned to the diagnostic categories mentioned at 6.1. or categorized as healthy. No randomization is planned.

7.4 Criteria for withdrawal / discontinuation of subjects

Patients are allowed to withdraw their participation at any point of time without communicating their reason. Investigators as well are allowed to exclude enrolled participants from the ongoing study if participants are non-compliant or if they see potentially harming constellations.

Data from patients who withdrew their participation will be made completely anonymous.

8. CLINICAL INVESTIGATION INTERVENTION

8.1 Identity of the medical device under investigation

Optical coherence tomography is a safe, non-invasive and worldwide spread imaging technique, using light in the near-infrared spectral range to produce a cross-sectional tissue images. The OCT is used in daily routine and an established diagnostic tool for detecting and diagnosing retinal and optic nerve diseases. The assessment of OCT images of both eyes takes about 5 minutes

8.1.1 Experimental Intervention (medical device)

The SPECTRALIS HighRes-OCT ® is a non-contact ophthalmic imaging device for the eye to investigate anatomy and has received CE mark. SPECTRALIS HighRes-OCT® has a confocal laser scanning and an optical coherence tomography. The device is indicated for visualizing posterior ocular structures including, but not limited to, retina, retinal nerve fiber layer, ganglion cell plus inner plexiform layer, macula, optic nerve head, vitreous and choroid.

To produce an image a laser beam is focused on the retina. The intensity of the reflected light or of the emitted fluorescent light at each point is measured with a light sensitive detector. Light reflected or emitted outside of the adjusted focal plane is suppressed in a confocal optical system, resulting in high contrast images. The latter acquires furthermore a layer-by-layer three dimensional image. This system allows to image patients with non-dilated pupils, which is especially important in a daily routine. The laser sources of the device emit laser light with four different wavelengths:

- A blue laser diode with a wavelength of 486 nm is used to excite the fluorescein or the intrinsic autofluorescence. A barrier filter at 500 nm separates excitation and fluorescence light. The same wavelength without the barrier filter is used to create red-free images.
- A diode laser at 730 nm wavelength produces infrared reflectance images.
- A diode laser at 518 nm wavelength.

The SPECTRALIS ® uses spectral domain optical coherence tomography (SD-OCT) technology, also referred to as Fourier domain OCT (FD-OCT). The beam of a super luminescence diode (SLD) scans across the retina to produce a cross sectional B-scan image. To create high spatial resolution three dimensional images of the retina, B-scans as close as 11 microns to each other can be acquired.

[figure not shown]

Fig. 1: SPECTRALIS HighRes-OCT

- | | |
|--|-------------------------------------|
| ① External fixation light | ⑧ Filter wheel |
| ② Forehead rest | ⑨ Focus knob; not shown |
| ③ Head rest column with red canthus marks | ⑩ Screw for adjusting the chin rest |
| ④ Chin rest | ⑪ Joystick |
| ⑤ Touch panel with ART/Sensitivity knob | ⑫ Set screw; not shown |
| ⑥ Camera head | |
| ⑦ SPECTRALIS HighRes-OCT standard objective lens | |

The infrared beam of the SLD has a central wavelength of 850 nm. The SPECTRALIS utilizes two separate beams of light to capture two images simultaneously. One beam constantly tracks and images the fundus. It also acts as a reference, guiding the OCT beam. Active eye tracking “locks” the OCT to the fundus, providing precise alignment of blood vessels and fundus image. Active eye tracking is of critical importance in 3D volume scans which are susceptible to eye motion artifact.

The SPECTRALIS HighRes-OCT[®] is a retinal imaging device intended to be used as a non-contact, imaging instrument for in vivo viewing, axial cross-sectional imaging, and three-dimensional imaging of ocular structures. No cases have been identified in which the product's failure to perform

its intended clinical functions would result in unacceptable risk. The subject will be imaged according to the SOP set forth in the user manual of the device. No dye is necessary when performing

8.1.2 Control Intervention (standard/routine/comparator)

The routine (standard) examinations to investigate retinal pathologies are spectral-domain optical coherence tomography (SD-OCT), color fundus imaging and fluorescein angiography. These investigations are routinely performed in daily clinical practice. SD-OCT and color fundus imaging are noncontact and dye free imaging methods. Intravenous Fluorescein angiography (IVFA) is a technique for examining the circulation of the retina and choroid using a fluorescent dye and a specialized camera. The nurse will ensure intravenous access with a venflon intravenous cannulation device. Just prior to obtaining images 500 mg (1 ampoule of 5 mL) of fluorescein (Fluoresceine 10% Faure, Novartis Pharma AG, Basel, Switzerland) will be injected intravenously. Then an angiogram is obtained by photographing the fluorescence emitted after illumination of the retina with blue light at a wavelength of 490 nanometers. This test uses the dye tracing method. In daily routine patient consent is obtained to perform fluorescein angiography. If there is known hypersensitivity or allergy to fluorescein no fluorescein angiography is performed.

The fluorescein dye also reappears in the patient urine, causing the urine to appear darker, and sometimes orange. It can also cause discoloration of the saliva. Fluorescein angiography is one of several health care applications of this dye, all of which have a risk of severe adverse effects, such as allergic responses.

8.1.3 Labelling and Supply (re-supply)

Not applicable.

8.1.4 Storage Conditions

Not applicable.

8.2 Discontinuation or modifications of the intervention

Since the procedure consists of a simple image capture on a single visit, lasting approximately 230-60 seconds and since the procedure is not related to a risk for the participants, the point 8.2 is not applicable for this study. If a participant wants to stop the process at any time, their decision will be respected.

